6.11 Concomitant treatment

All prescription medications, over-the-counter drugs and significant non-drug therapies (including physical therapy and blood transfusions) administered or taken within the timeframe defined in the entry criteria prior to the start of the study and during the study, must be recorded on the Concomitant medications/ Significant non-drug therapies section of the CRF.

Medication entries should be specific to trade name, the single dose and unit, the frequency and route of administration, the start and discontinuation date and the reason for therapy.

All concomitant diseases and conditions will be treated in accordance with prevailing medical practice.

7 Study completion and discontinuation

7.1 Study completion and post-study treatment

Each subject will be required to complete the study in its entirety and thereafter no further study treatment will be made available to them.

Study completion is defined as when the last subject completes their Study Completion visit, and any repeat assessments associated with this visit have been documented and followed-up appropriately by the Investigator, or in the event of an early study termination decision, the date of that decision.

All randomized and/or treated subjects will have a safety follow-up call conducted 14 days after last administration of study treatment. The information collected is kept as source documentation. All SAEs reported during this time period must be reported as described in [Section 9.2](#) and the Site Operations Manual. Documentation of attempts to contact the subject should be recorded in the source documentation.

Continuing care should be provided by investigator and/or referring physician based on subject availability for follow-up. This care may include:

- promote compliance for the visits schedule for urine samples collection
- promote compliance for data entry in TLFB cocaine , as well as TLFB alcohol

7.2 Discontinuation of study treatment

Discontinuation of study treatment for a subject occurs when study treatment is stopped earlier than the protocol planned duration. Discontinuation of study treatment can be decided by either the subject or the investigator.

Discontinuation of study treatment and patient withdrawal will be at the discretion of the Investigator, under the following circumstances:

- Moderate and persistent (>24 hours) CNS related AEs, i.e.. behavioral effects and/or neurological adverse effects, in the opinion of the Investigator as suspected to be related to AFQ056 study medication
- Missed > 6 consecutive visits
- Missed > 7 consecutive doses of study medication during the fixed-dose treatment period or a total of more than 14 cumulative doses at any time during the study
- Use any of prohibited treatment

* If a liver or renal event occurs, follow guidelines outlined in [Appendix 2](#) regarding discontinuation of study treatment.

Study treatment **must be** discontinued under the following circumstances:

- Subject/guardian decision - subjects may choose to discontinue study treatment for any reason at any time.
- The investigator believes that continuation would negatively impact the safety of the subject or the risk/benefit ratio of trial participation.
- Any protocol deviation that results in a significant risk to the subject's safety.
- Pregnancy (see [Section 8.6](#) (Safety) and [Section 9.6](#) (Pregnancy reporting)).
- Severe withdrawal syndrome or need for detoxification

For all discontinued patients, the follow-up period is to be followed, where possible.

Patients, who discontinue study treatment must NOT automatically be considered withdrawn from the study. Patients who discontinue study treatment before completing the study, and those who prematurely withdraw from the study for any reason, must be scheduled for a visit approximately 1 week after the last dose of study medication, at which time all of the assessments listed for the final visits (End of Study visit) must be performed (see [Assessment schedule](#)).

After study treatment discontinuation, at a minimum, the following data should be collected at clinic visits or via telephone/email contact:

- new / concomitant treatments
- adverse events/Serious Adverse Events

If discontinuation of study treatment occurs, investigator must determine the primary reason for the subject's premature discontinuation of study treatment and record this information on the Dosage Administration CRF

For patients who are lost to follow-up (e.g.. those patients whose status is unclear because they fail to appear for study visits without stating an intention to withdraw), the investigator must show "due diligence" by documenting in the source documents steps taken to contact the patient, e.g. dates of telephone calls, registered letters, etc.

If a patient needs to be hospitalized either temporarily or permanently during the course of this study, the sponsor needs to be notified by the investigator and the sponsor will make a decision whether the patient can remain in the study or needs to be discontinued.

The appropriate personnel from the site and Novartis will assess whether study treatment should be discontinued for any patient whose treatment code has been broken inadvertently for any reason.

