9.1 Adverse events

An adverse event (AE) is any untoward medical occurrence (i.e., any unfavorable and unintended sign [including abnormal laboratory findings], symptom or disease) in a subject after providing written informed consent for participation in the study until the end of study visit. Therefore, an AE may or may not be temporally or causally associated with the use of a medicinal (investigational) product.

In addition, all reports of intentional misuse and abuse of the study treatment are also considered an adverse event irrespective if a clinical event has occurred. See [Section 9.5](#) for an overview of the reporting requirements.

The occurrence of adverse events must be sought by non-directive questioning of the subject at each visit during the study. Adverse events also may be detected when they are volunteered by the subject during or between visits or through physical examination finding, laboratory test finding, or other assessments.

Abnormal laboratory values or test results constitute adverse events only if they fulfill at least one of the following criteria:

- they induce clinical signs or symptoms,
- they are considered clinically significant,
- they require therapy.

Clinically significant abnormal laboratory values or test results should be identified through a review of values outside of normal ranges/clinically notable ranges, significant changes from baseline or the previous visit, or values which are considered to be non-typical in patients with underlying disease. Investigators have the responsibility for managing the safety of individual subject and identifying adverse events. Alert ranges for liver and kidney related events are included in [Appendix 1](#) and [Appendix 2](#), respectively.

For all completed scales/questionnaire described below, the Investigator will be required to review and examine responses which may indicate potential AEs or SAEs. The investigator should review not only the responses to the scale but also for any unsolicited comments written by the subject. If the occurrence of AEs or SAEs is confirmed, the physician should record the events as per instructions given in [Section 7](#). Investigators should not encourage the subjects to change the responses reported on the scale.

Adverse events should be recorded on the Adverse Events CRF under the signs, symptoms or diagnosis associated with them, and accompanied by the following information:

- AE severity grade (mild/moderate/severe):

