9.3 Liver safety monitoring

To ensure subject safety and enhance reliability in determining the hepatotoxic potential of an investigational drug, a standardized process for identification, monitoring and evaluation of liver events has to be followed.

Please refer to [Table 15-1-Appendix 1](#) for complete definitions of liver events.

Follow-up of liver events

Every liver event defined in [Table 15-1-Appendix 1](#) should be followed up by the investigator or designated personnel at the trial site, as summarized below. Additional details on actions required in case of liver events are outlined in [Table 15-2 - Appendix 1](#).

- Repeating liver chemistry tests (ALT, AST, TBL, PT/INR, ALP and G-GT) to confirm elevation within 48-72 hours.

These liver chemistry repeats should always be performed using the central laboratory, with the results provided via the standard electronic transfer. If results will not be available from the central laboratory within 24 hours, then the repeats can also be performed at a local laboratory to monitor the safety of the subject. If a liver event is subsequently reported, any local liver chemistry tests previously conducted that are associated with this event should have results reported on the unscheduled local laboratory CRF.

- If the initial elevation is confirmed, close observation of the subject will be initiated, including consideration of treatment interruption if deemed appropriate.
- Discontinuation of the investigational drug (refer to [Section 7.2](#) (Discontinuation of study treatment), if appropriate
- Hospitalization of the subject if appropriate
- Causality assessment of the liver event

Thorough follow-up of the liver event should include

- Repeating liver chemistry tests two or three times weekly. Testing should include ALT, AST, ALP, PT/INR, and GGT. If total bilirubin is elevated > 2 x ULN, fractionation into direct and indirect bilirubin is required. To rule out muscular origin of transaminase elevations, CPK should be measured along with liver chemistry tests. Frequency of retesting can decrease to once a week or less if abnormalities stabilize or the study drug has been discontinued and the subject is asymptomatic. Retesting should be continued up to resolution.
- Obtaining a more detailed history of symptoms and prior or concurrent diseases.

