The United Nations Office on Drugs and Crime (UNODC) (2016) UNODC-WHO International Standards for the Treatment of Drug Use Disorders.

15 Appendix 1: Liver Event Definitions and Follow-up Requirements

Table 15-1 Liver Event Definitions

Definition	Thresholds
Potential Hy's law cases	
 ALT or AST > 3 × ULN and TBL > 2 × ULN without initial increase in ALP to > 2 × ULN
ALT or AST elevation with coagulopathy	
 ALT or AST > 3 × ULN and INR > 1.5 (in the absence of anticoagulation)
ALT or AST elevation accompanied by symptoms	
 ALT or AST > 3 × ULN accompanied by (general) malaise, fatigue, abdominal pain, nausea, or vomiting, or rash, or eosinophilia
Isolated ALT or AST elevation	
 ALT or AST > 8 × ULN 5 × ULN < ALT/AST ≤ 8 × ULN 3 × ULN < ALT/AST ≤ 5 × ULN
Isolated ALP elevation	
 ALP > 2 × ULN (in the absence of known bone pathology)
Others	
 Any clinical event of jaundice (or equivalent term) Any adverse event potentially indicative of liver toxicity

Table 15-2 Actions required for Liver Events

Criteria	Actions required
Potential Hy's Law case	
ALT or AST elevation with coagulopathy	
 Discontinue the study treatment immediately
ALT or AST elevation accompanied by symptoms	
 Hospitalize, if clinically appropriate Establish causality
Isolated ALT or AST elevation > 8 × ULN	
 Complete CRFs per liver event guidance*
Jaundice	
 If confirmed, consider interruption or discontinuation of study drug
Isolated ALT or AST elevation > 5 to ≤ 8 × ULN	
 If elevation persists for more than 2 weeks, discontinue the study drug Establish causality Complete CRFs per liver event guidance*
Isolated ALT or AST elevation > 3 to ≤ 5 × ULN (patient is asymptomatic)	
 Monitor liver chemistry tests two or three times weekly Repeat liver chemistry tests within 48-72 hours
Isolated ALP elevation	
 If elevation is confirmed, measure fractionated ALP; if >50% is of liver origin, establish hepatic causality Complete CRFs per liver event guidance* Consider study treatment interruption or discontinuation

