Any AE potentially indicative of liver toxicity	
 Hospitalize if clinically appropriate Complete CRFs per liver event guidance*

*Liver event guidance for CRF completion is available in the Site Operations Manual

Table 15-3 Exclusion of underlying liver disease

Disease	Assessment
Hepatitis A, B, C, E	
• IgM anti-HAV; HBSAg, IgM anti-HBc, HBV DNA; anti-HCV, HCV RNA, IgM & IgG anti-HEV, HEV RNA
CMV, HSV, EBV infection	
• IgM & IgG anti-CMV, IgM & IgG anti-HSV; IgM & IgG anti-EBV
Autoimmune hepatitis	
• ANA & ASMA titers, total IgM, IgG, IgE, IgA
Alcoholic hepatitis	
• Ethanol history, GGT, MCV, CD-transferrin
Nonalcoholic steatohepatitis	
• Ultrasound or MRI
Hypoxic/ischemic hepatopathy	
• Medical history: acute or chronic CHF, hypotension, hypoxia, hepatic venous occlusion. Ultrasound or MRI.
Biliary tract disease	
• Ultrasound or MRI, ERCP as appropriate.
Wilson disease	
• Caeruloplasmin
Hemochromatosis	
• Ferritin, transferrin
Alpha-1-antitrypsin deficiency	
• Alpha-1-antitrypsin

16 Appendix 2: Specific Renal Alert Criteria and Actions

Table 16-1 Specific Renal Alert Criteria and Actions

Criteria	Action required
Serum creatinine (sCr) increase 25 – 49% compared to baseline	
 Consider causes and possible interventions Follow up within 2-5 days
Serum creatinine increase > 50%	
 Consider causes and possible interventions Repeat assessment within 24-48h if possible Consider drug interruption or discontinuation unless other causes are diagnosed and corrected Consider hospitalization and specialized treatment
Protein-creatinine or albumin-creatinine ratio increase \geq 2-fold	
or	
new onset dipstick proteinuria \geq 1+	
 Consider causes and possible interventions Assess serum albumin & serum protein
or	
Albumin-creatinine ratio (ACR) \geq 30 mg/g or \geq 3 mg/mmol;	
 Repeat assessment to confirm Consider drug interruption or discontinuation unless other causes are diagnosed and corrected
or	
Protein-creatinine ratio (PCR) \geq 150 mg/g or >15 mg/mmol	

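### Protocol Section 7.2 sends liver events to the renal appendix for discontinuation guidance, and Section 6.6 bans the one interruption that Section 8.6.8 requires

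*Protocol*

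**What the plan says.** On liver events, the protocol gives these instructions:

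- Section 7.2 has a list of reasons for which the investigator may stop treatment. Directly below it stands: "If a liver or renal event occurs, follow guidelines outlined in [Appendix 2](#) regarding discontinuation of study treatment". A second list, of mandatory stops, follows.
- The appendix it names is headed "16 Appendix 2: Specific Renal Alert Criteria and Actions".
- Section 9.1 assigns the appendices differently: "Alert ranges for liver and kidney related events are included in [Appendix 1](#) and [Appendix 2](#), respectively".
- Section 9.3, the liver section, introduces its follow-up list with: "Additional details on actions required in case of liver events are outlined in [Table 15-2 - Appendix 1". One bullet in that list reads: "Discontinuation of the investigational drug (refer to [Section 7.2](#) (Discontinuation of study treatment), if appropriate".
- Table 15-2 in Appendix 1 contains two instructions that leave no discretion: "Discontinue the study treatment immediately" and "If elevation persists for more than 2 weeks, discontinue the study drug".

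On interruptions, Section 6.6 is a single sentence that disallows dose adjustments and interruptions and names no exception. Section 8.6.8 says that a positive urine pregnancy test calls for treatment to be interrupted at once, until a serum test has been done and is negative.

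**The concern.** Section 7.2 is where a site looks when deciding whether a patient must come off drug. For a liver event it leads to tables on creatinine, urinary protein, glucose and blood, where stopping is at most something to consider. A site that goes no further does not see that some liver findings require a stop.

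Liver events are plausible in this population. Exclusion criterion 12 admits patients with AST or alkaline phosphatase up to 5 × ULN. Table 15-1 counts AST above 3 × ULN, and alkaline phosphatase above 2 × ULN without known bone pathology, as liver events.

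The interruption ban raises a different problem. Urine pregnancy tests are scheduled several times during treatment. A site with a positive result must either break 6.6 by holding the drug or break 8.6.8 by continuing it. At stake are clear safety instructions and avoidable protocol deviations, not the efficacy analysis.

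**Working it through.** No arithmetic is needed beyond counting, and the documents give no figure to reproduce. The check sets the sections side by side.

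**1. Does Appendix 2 contain anything on the liver?** Table 16-1 has five criteria: a creatinine rise of 25–49%, a creatinine rise above 50%, a group of protein and albumin findings, new glucosuria, and new hematuria. Liver criteria: 0 of 5. Discontinuation appears against two of the five, each time as something to consider. Table 16-2 covers renal follow-up. The reference in 7.2 is therefore wrong for liver events and right for renal events.

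**2. Does 7.2 cover liver events in another way?** Its mandatory list has five items: the subject's decision, the investigator's safety judgement, a deviation that puts safety at risk, pregnancy, and severe withdrawal or need for detoxification. None names a liver event. The nearest is "The investigator believes that continuation would negatively impact the safety of the subject or the risk/benefit ratio of trial participation". That clause can cover a liver event, but only after the investigator has formed that view. Table 15-2 does not wait for a view.

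**3. Can a site reach the liver rules?** Yes, by two routes: 9.1 names Appendix 1 for the liver, and 9.3 names Tables 15-1 and 15-2. There is also a path that fails: the discontinuation bullet in 9.3 leads to 7.2, which leads to Appendix 2.

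**4. Which interruption instructions meet the ban in 6.6?**

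- Mandatory: 8.6.8, one entry.
- To be considered: 9.3 (one), Table 15-2 (two), Table 16-1 (two), so 1 + 2 + 2 = 5 entries.
- Generic: 9.1 includes interruption in a menu of possible responses to an adverse event, one entry.

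The total is 1 + 5 + 1 = 7 mentions, of which one conflicts directly. The four table entries offer interruption or discontinuation, so a site can satisfy both the table and 6.6 by discontinuing or, having considered it, by doing neither. The 9.3 entry applies only where judged appropriate.

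**5. Is the 8.6.8 conflict real?** If the serum test is positive, 7.2 and 9.6 require a permanent stop, which 6.6 does not forbid. If it is negative, 8.6.8 has already required a temporary hold that ends with that result. A temporary hold is exactly what 6.6 disallows, and discontinuing permanently would not be what 8.6.8 describes.

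**The case against.** The strongest reply is that nothing is missing. Table 15-2 sets out required actions and binds whether or not 7.2 repeats it. The dedicated liver section cites it by number, and a reader who follows the wrong reference meets a heading that says renal, directly after the liver appendix. This stands, and it is why the point is minor. It does not make the reference in 7.2 correct.

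A second reply is that 7.2 handles organ events by pointing to an appendix, and renal events are not in its mandatory list either. This also stands. A reader might infer that the mandatory list is defective because it omits the Table 15-2 stops, but once the reference is right there is no need to copy them in.

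A third reply is that Section 13.1 expects the investigator to take immediate action for a subject's safety even where it departs from the protocol. So a site would hold the drug after a positive pregnancy test despite 6.6. That limits the practical harm. It still leaves a step that the protocol itself requires to be treated as a deviation from it.

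Last, the seven mentions of interruption might be read as seven contradictions. They are not: five are optional, and the 9.1 entry is a general list that also includes dose increases and reductions.

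**Conclusion.** Two wording errors stand, both minor.

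- Section 7.2 gives the wrong appendix for liver events, and the back-reference in 9.3 leads into that error.
- Section 6.6 conflicts directly with one mandatory instruction, in 8.6.8, and sits awkwardly with five optional ones.

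Three stronger readings are tempting, and the documents do not support them. The liver stopping rules are not absent or contradicted, since Table 15-2 contains them and 9.1 and 9.3 lead there. Section 6.6 does not block a liver stop, because it bans interruptions and not permanent discontinuation. Nothing in the documents shows an effect on the primary variable.

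The conclusion rests on running text and on legible instructions in the tables. Row alignment in the available copy of Table 15-2 is not fully readable, so the exact rows covered by the immediate stop are left open; the finding does not depend on them. The documents give no expected number of liver events or positive pregnancy tests, so no frequency is claimed.

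**What to change.** Two changes of wording in a protocol amendment:

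- **Section 7.2.** Refer liver events to Appendix 1 (Table 15-2) and renal events to Appendix 2, and state that the stops in Table 15-2 are mandatory. The bullet in 9.3 that points to 7.2 then leads to the right place without being edited.
- **Section 6.6.** Keep the general ban and add an exception for safety interruptions under Section 8.6.8, Section 9.3 and Appendices 1 and 2.

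Sections 9.1 and 9.3 can stay as they are, and the rows of Table 15-2 need not be copied into 7.2. The cost is the amendment text and its approval under Section 13.1, with no new tests, visits or staff.

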7.3 Withdrawal of informed consent

Subjects may voluntarily withdraw consent to participate in the study for any reason at any time.

Withdrawal of consent from the study is defined as when a subject:

- Does not want to participate in the study anymore and
- Does not want any further visits or assessments and
- Does not want any further study related contacts and
- Does not allow analysis of already obtained biologic material.

In this situation, the investigator must make every effort (e.g. telephone, e-mail, letter) to determine the primary reason for the subject's decision to withdraw his/her consent and record this information.

Study treatment must be discontinued and no further assessments conducted, and the data that would have been collected at subsequent visits will be considered missing.

Further attempts to contact the subject are not allowed unless safety findings require communicating or follow-up.

7.4 Lost to follow-up

For subjects whose status is unclear because they fail to appear for study visits without stating an intention to discontinue or withdraw, the investigator should show "due diligence" by documenting in the source documents steps taken to contact the subject, e.g. dates of telephone calls, registered letters, etc. A subject cannot be formally considered lost to follow-up until his/her scheduled end of study visit would have occurred.

7.5 Study stopping rules

The study will be placed "on hold" if any of the following criteria are met, and no new patients will be randomized, pending a safety review, if:

- at least 1 or more patients exhibits a life threatening or persisting/significant disabling SAEs such as confusion, mood alteration, somnolence and/or psychosis, that are deemed related to the study medication by the investigator, and confirmed to be on active treatment when blind is broken for that patient
- at least 3 and more patients exhibit at least one severe AE such as confusion, delirium, mood alteration (euphoria or agitation) and/or psychosis (hallucinations or delusions) which interfere with their activities of daily living, require medical intervention and medical supervision, and are deemed related to the study medication by the investigator, and confirmed to be on active treatment when blind is broken for that patient
- The Sponsor considers that the number and/or severity of AEs, abnormal safety monitoring tests or abnormal laboratory findings justify putting the study on hold.

Following the safety review, the study may continue, if the Investigator and Sponsor agree it is safe to proceed.

